Attachment 10. Protocol JOBA Toxicity-Band Method for Phase 1 Dose Escalation

The need to minimize the number of patients treated below the biological active dose and the understanding of LY3076226 from earlier nonclinical and clinical studies supports a more efficient dose-escalation design for Study JOBA. Therefore, the Bayesian model-based method is used in this trial to determine the next dose level, based on the predicted probabilities of DLT rates. The exact dose-escalation increment will be determined by the investigators and Lilly CRP/CRS and may be different from the model recommendation. This section introduces the background of a model-based dose-escalation method and toxicity-band design (Neuenschwander et al. 2008) and describes the key elements for this trial. Simulation results from the toxicity-band design are presented. These results are also compared with that from the simulation of traditional 3+3 design to demonstrate the benefit of implementing a toxicity-band design in this trial. Fixed and Adaptive Clinical Trial Simulator (FACTS) software version 3.5 is used for all the simulations.

Introduction to Continual Reassessment Method (CRM) Approaches

The continual reassessment method (CRM; O'Quigley et al. 1990) is the first Bayesian model-based approach developed for dose-escalation studies. Compared to the traditional 3+3 design that only used current dose-level DLT data to estimate the MTD, CRM utilizes prior dose toxicity information and all available DLT data to effectively estimate the MTD. To improve the operating characteristics of CRM, Goodman et al. (1995), among others, have proposed modified CRM (MCRM) procedures to make the model-based designs more acceptable in practice. The major modifications include:

- Always start at the lowest dose level.
- Limit the escalation increment.
- Escalate by cohorts rather than single patients.

Babb et al. (1998) proposed the escalation-with-overdose-control method (EWOC) that directly controls the probability of overdosing during dose escalation. EWOC is also a CRM-type method. During the escalation, EWOC selects the next dose such that the predicted probability that the new dose exceeds the MTD is equal to a prespecified feasibility bound $\alpha=0.25$. The connection between CRM and EWOC is that CRM typically uses the middle (mean or median) of the MTD's posterior distribution as the next recommended dose, whereas EWOC uses the 25th percentile. Therefore, EWOC is a more conservative method than the original CRM method.

Toxicity-Band Design

Neuenschwander et al. (2008) extended the concept of EWOC (Babb et al. 1998) and proposed considering the uncertainty of the posterior distributions and using interval estimates to make the dose recommendation, herein referred to as the toxicity-band design.

The Model

A 2-parameter logistic model is used to model the relationship between dose and probability of a DLT:

$$\text{logit}\{p(d)\} = \alpha + \beta \log\left(\frac{d}{d^*}\right), \quad \beta > 0. \quad (1.1)$$

In the model, d is the true dose and $p(d)$ is the probability of a DLT at dose d . d^* is the reference dose, such that α is interpreted as the log-odds of a DLT at d^* .

Toxicity Band

The probability of a DLT is categorized to 4 bands:

- Underdosing: $p(d)$ in $(0, 0.20]$
- Targeted toxicity: $p(d)$ in $(0.20, 0.33]$
- Excessive toxicity: $p(d)$ in $(0.33, 0.60]$
- Unacceptable toxicity: $p(d)$ in $(0.60, 1.00]$

Overdosing is defined as $p(d) > 0.33$.

Dose Recommendation

During the escalation, after each cohort of patients, the following will be done:

1. Calculate the posterior probabilities of the 4 toxicity bands for each dose.
2. Exclude the doses such that the posterior probabilities of overdosing are larger than 0.25 (overdosing control criteria). The remaining doses are the ones that satisfy the overdose control criteria.
3. Among the remaining doses, the dose with the highest posterior probability in the targeted toxicity band will be the model recommendation of the next dose.

The data will be evaluated on an ongoing basis until the MTD is determined. Once the MTD has been identified, a discussion between the sponsor and investigators may occur in order to treat additional patients at intermediate doses below the MTD.

Dose Range and Reference Dose

It is assumed that the starting dose level for the toxicity-band method is 1.6 kg/mg. Based on the preclinical data, the highest dose level that will be explored in this study is 5 mg/kg and the reference dose in model (1.1) is chosen as $d^* = 5$ mg/kg.

The Prior Distribution on Model Parameters

A quantile-based uninformative prior (Neuenschwander et al. 2008) is used to derive a bivariate-normal prior on $(\alpha, \log\beta)$. Based on preclinical experience of LY3076226, the median probability of DLT for the dose levels from 1.6 mg/kg to 5 mg/kg was determined as in Table 1 of this attachment. Any intermediate dose level within the starting doses to 5 mg/kg can be explored.

Table 1. Prior Median Probability of DLT at Each Dose Level

[figure not shown]
Dose (mg/kg)	Median Probability of DLT
1.6	0.075
2.4	0.125
3.2	0.175
4	0.225
5	0.35

Abbreviation: DLT = dose-limiting toxicity.

For each dose, the minimally informative unimodal Beta distribution (a,b) is derived as the prior distribution for the probability of DLT, so that the operating characteristics of the model are robust to the selected prior distribution of DLT:

- For median probability of DLT <0.5 , $b=1$ and $a(<1)$ are tuned to match the median.
- For median probability of DLT >0.5 , $a=1$ and $b(<1)$ are tuned to match the median.

Figure 1 shows the median and the 95% CI of the prior distribution of the DLT rate at each dose level.

Abbreviations: CI = confidence interval; DLT = dose-limiting toxicity.

Figure 1. The prior distribution of DLT rate at each dose level.

A bivariate normal distribution was derived on $(\alpha, \log\beta)$ that stochastically gives the best fit to the 2.5%, 50%, and 97.5% quantiles of the prior probability of DLT at each dose. The parameters $(\alpha, \log\beta)$ have a bivariate normal distribution with mean= $(-0.69, 0.39)$, SD= $(1.95, 1.05)$, and $\rho=-0.25$.

Simulation Studies

Simulations were performed under different scenarios of possible dose-toxicity relationships to investigate the operational characteristics of the toxicity-band versus traditional 3+3 design:

- 3-patient cohorts starting from the lowest dose.
- Maximum number of patients: 24 for toxicity-band method and 30 for traditional 3+3 method.
- Stopping rules for toxicity-band method: maximum sample size reached or at least 6 patients have been treated at the recommended next dose level.

Assuming that the starting dose level is 1.6 mg/kg, 4 scenarios were considered to represent a wide range of possible dose-toxicity relationships as shown in Figure 2 and Table 2 of this attachment. DLT rates for the starting dose level are chosen to take into account single-patient cohorts before. The true DLT rate of the MTD is set at 20% to 33% across scenarios. Scenarios 1 and 2 have MTD at 5 mg/kg, and Scenarios 3 and 4 have MTD at 4 mg/kg. When the dose-toxicity curve is steep around MTD, the concern is the risk of overdosing; when the dose-toxicity curve is flat around MTD, the concern is underdosing. The simulation studies will assess the performance of the toxicity-band method and compare it to the traditional 3+3 focusing on these concerns.

[figure not shown]

Figure 2. The dose-toxicity relationships under each scenario.

Table 2. The Dose-Toxicity Relationships under Each Scenario Starting from 1.6 mg/kg

Dose (mg/kg)	Scenarios			
	1	2	3	4
1.6	0.05	0.075	0.1	0.13
2.4	0.08	0.135	0.15	0.19
3.2	0.12	0.185	0.2	0.245
4	0.18	0.235	0.3	0.3
5	0.28	0.28	0.42	0.38

One thousand (1000) simulations were conducted under each scenario to investigate the operational characteristics of toxicity-band and traditional 3+3 methods. The results are summarized in Table 3 of this attachment.

Table 3. Comparison of Toxicity-Band and Traditional 3+3 Methods

Rate of Selected as MTD for Each Dose (mg/kg)	Scenarios							
	1		2		3		4	
	TB	3+3	TB	3+3	TB	3+3	TB	3+3
1.6	0.079	0.08	0.185	0.192	0.25	0.258	0.392	0.394
2.4	0.078	0.119	0.155	0.199	0.209	0.208	0.195	0.233
3.2	0.134	0.183	0.122	0.214	0.257	0.242	0.196	0.177
4	0.305	0.285	0.198	0.177	0.22	0.209	0.143	0.135
5	0.404	0.333	0.34	0.218	0.064	0.083	0.074	0.071
Rate of selecting Ph2 dose below true MTD	0.596	0.667	0.66	0.782	0.611	0.671	0.783	0.818
Rate of selecting Ph2 dose above true MTD	0	0	0	0	0.064	0.083	0.074	0.071
Rate of DLT events during the trial	0.16	0.14	0.20	0.19	0.22	0.22	0.26	0.25
Mean # subjects	17.5	16.4	16.0	14.9	14.2	14.0	12.8	12.4

Abbreviations: TB = toxicity-band method; DLT = dose-limiting toxicity; MTD = maximum tolerated dose. Results based on 1000 simulations.

The traditional 3+3 design is generally conservative and has a higher rate of selecting a dose level below the true MTD to be recommended for future Phase 2 studies, increasing the risk of under-dosing and failure rate of Phase 2 studies. The toxicity-band method is slightly more aggressive in general and has a lower rate of MTD selection below the true level, and a higher rate of MTD selection at the true level. The mean percentages of a DLT event in each scenario are in general higher in the toxicity-band method, but strictly kept below the prespecified overdosing control criterion at 0.25.

[figure not shown]
Examples

Examples from Scenario 1 and Scenario 4 are provided here to illustrate how the toxicity-band method operates under certain circumstances.

Example 1

Scenario 1 has a true MTD at 5 mg/kg with a DLT rate of 0.28 in Table 2. With a slowly increasing relationship between the dose level and the DLT rate, patients could be assigned to dose levels under MTD and cause underdosing when DLT occurs in the first few cohorts.

With the toxicity-band method, the next recommended dose level is 5 mg/kg after the 15th patient is treated (Figure 3a), although 2 DLTs are observed at 4 mg/kg, and 4 mg/kg will be declared as MTD after 21 patients are treated. However, using the traditional 3+3 method, dose de-escalation will be conducted after the 12th patient, since 2 DLTs have already been seen at the current dose level. The toxicity-band method has also allocated more patients at the MTD dose level.

[figure not shown]
Abbreviation: MTD = maximum tolerated dose.

Figure 3a. A case study for Scenario 1.

Example 2

Scenario 3 has a true MTD at 4 mg/kg with a DLT rate of 0.3 in Table 2. With a relatively steep increasing relationship between the dose level and the DLT rate, patients could be assigned to dose levels above MTD and cause overdosing when few DLT occurs in the first few cohorts.

With the toxicity-band method, the next recommended dose level is still 4 mg/kg after the 18th patient is treated (Figure 3b), although 1 DLT is observed at 4 mg/kg. As 6 patients have already been treated at the next recommended dose level, the dose escalation is ceased and 4 mg/kg will be declared as MTD. However, using the traditional 3+3 method, the lower dose, 3.2 mg/kg, will be selected as MTD. Therefore, the selected MTD from the toxicity-band method is closer to the true MTD comparing to the traditional 3+3 method.

Abbreviation: MTD = maximum tolerated dose.

Figure 3b. A case study for Scenario 3.

Summary

As a conclusion, based on the simulation studies on a variety of scenarios and the illustrative examples, the toxicity-band method is slightly more aggressive than the traditional 3+3 design, and therefore provides a lower underdosing rate and a higher MTD selection rate, with a well-controlled overdosing rate at a prespecified criterion. Therefore, the modified 3+3 method that incorporates the principles of the toxicity-band method will be used in this study rather than the traditional 3+ 3 escalation paradigm.

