If, during dose escalation, a situation presents itself that is not described above, Lilly CRP/CRS and investigators will determine the best method to select the appropriate dose for the patient(s) involved, using all available information. The decision will be documented in writing. No dose escalation can occur without prior discussion and agreement between the site-specific investigator and the Lilly CRP/CRS. Written notification will be sent to the site specifying the dose to be used for each patient at each dose level.

Table JOBA.3. Example of LY3076226 Dose Levels for Part A

Cohort	LY3076226 Dose Level (mg/kg)
1	0.2
2	0.4
3	0.8
4	1.6
5	2.4
6	3.2
7	4.0
8	5.0

Based on the ongoing safety reviews, modifications to the dose-escalation strategy or other design elements may be made via protocol amendment to ensure patient safety.

7.2.3. Dose Confirmation in Patients with Known Alterations of FGFR3 (Parts B and C)

Once the MTD has been defined in Part A, Parts B (urothelial carcinoma) and C (other malignancies) will be activated and will enroll up to approximately 15 patients who have known alterations of FGFR3, to further define the safety and tolerability of LY3076226 and to characterize the exploratory biomarker assays. The dose of LY3076226 in Parts B and C will not exceed the MTD of LY3076226, as defined during dose escalation in Part A. The exact sample size of this cohort will be dependent on the number of patients who have known FGFR3 alterations treated at the MTD during dose escalation in Part A, and will be adjusted so that a total of approximately 15 patients will be treated.

If a DLT-equivalent toxicity occurs in one third or more of patients during Cycle 1 (with a minimum of 6 patients enrolled), the enrollment of new patients will cease until the Lilly CRP/CRS and investigators assess the severity and nature of the toxicities. A data review will be performed to determine whether to continue at the current LY3076226 dose or whether the dose of LY3076226 should be reduced. The toxicity-band method used in the dose-escalation phase will be updated with the additional data observed in Parts B and C to confirm the MTD selection and/or to inform any need to further refine the MTD. This decision will be documented in writing.

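### Table 3's toxicity-band results cannot be reproduced from Attachment 10, which does not say what happens when no dose meets the 0.25 limit

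*Protocol*

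**What the plan says.** Attachment 10, Dose Recommendation, sets out what the model does after each cohort. Step 2: "Exclude the doses such that the posterior probabilities of overdosing are larger than 0.25 (overdosing control criteria". Step 3: "Among the remaining doses, the dose with the highest posterior probability in the targeted toxicity band" becomes the recommendation. Overdosing means a DLT probability above 0.33.

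Under Dose Range and Reference Dose: "It is assumed that the starting dose level for the toxicity-band method is 1.6" mg/kg. Under Simulation Studies the design is "3-patient cohorts starting from the lowest dose", with at most 24 patients for the toxicity-band method. The rules for ending a run are: "Stopping rules for toxicity-band method: maximum sample size reached or at least 6 patients have been treated at the recommended next dose level". The earlier single-patient cohorts appear only through the choice of true rates: "DLT rates for the starting dose level are chosen to take into account single-patient cohorts before". The results are in Table 3: "One thousand (1000) simulations were conducted under each scenario to investigate the operational characteristics of toxicity-band and traditional 3+3 methods".

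Section 10.1 and the Summary of Attachment 10 rely on Table 3 to say that, compared with 3+3, the method underdoses less and selects the MTD more often, with overdosing controlled.

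For the trial itself, Section 7.2.2.3 adds: "If, during dose escalation, a situation presents itself that is not described above, Lilly CRP/CRS and investigators will determine the best method", with the decision documented in writing.

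**The concern.** Step 3 needs at least one dose to survive step 2. If none does, there is no recommended next dose. The second stopping rule then has nothing to act on, and the first applies only at 24 patients. A study team can resolve this by discussion, but a simulator needs a coded instruction, and none is printed. If the situation is common in the simulated trials, Table 3 depends on that instruction. At stake is whether the operating characteristics used to justify the method over 3+3 belong to the rule as written.

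**Working it through.** **Inputs, all from Attachment 10.** Model: logit p(d) = α + β log(d/5). Prior: (α, log β) bivariate normal, means (-0.69, 0.39), SDs (1.95, 1.05), correlation -0.25. Grid: 1.6, 2.4, 3.2, 4, 5 mg/kg. First cohort: 3 patients at 1.6 mg/kg. True DLT rates at 1.6 mg/kg (Table 2): 0.05, 0.075, 0.10, 0.13.

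**Step 1: posterior after the first cohort.** With y DLTs in 3, the likelihood is proportional to p(1.6)^y × (1 - p(1.6))^(3 - y). Numerical integration over the prior gives P(p(d) > 0.33):

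| First cohort | 1.6 | 2.4 | 3.2 | 4 | 5 |
|---|---|---|---|---|---|
| 1/3 | 0.36 | 0.51 | 0.61 | 0.69 | 0.75 |
| 2/3 | 0.79 | 0.88 | 0.92 | 0.94 | 0.95 |

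After 3/3 every value is at least 0.97. Any DLT in the first cohort therefore excludes the whole grid.

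**Step 2: how often.** 1 - (1 - p)^3:
- Scenario 1: 1 - 0.95^3 = 14.3%
- Scenario 2: 1 - 0.925^3 = 20.9%
- Scenario 3: 1 - 0.90^3 = 27.1%
- Scenario 4: 1 - 0.87^3 = 34.1%

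**Step 3: what Table 3 prints.** The toxicity-band column for Scenario 1 is 0.079 + 0.078 + 0.134 + 0.305 + 0.404 = 1.000. The other three also sum to 1.000, so every run received an MTD.

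**Step 4: candidate rules for an empty set.** These were checked by enumerating all 3-patient-cohort paths, with escalation limited to one level, limited to 100%, or unlimited.

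- *Stop with no MTD, run kept in the denominator.* With one-level escalation, 15.9/25.1/32.0/41.4% of runs reach an empty set at some point. Columns could then sum only to 0.841/0.749/0.680/0.586, not 1.000.
- *Stop and count at 1.6 mg/kg.* Scenario 1 would select 1.6 mg/kg in at least 14.3% of runs. Expected count 1000 × 0.1426 = 142.6, SD √(1000 × 0.1426 × 0.8574) = 11.1, printed count 79, so z = (79 - 142.6)/11.1 = -5.7. The exact binomial probability is about 4 × 10^-10.
- *Stop and leave the run out of the denominator.* 1.6 mg/kg is selected in at most about 2/5/9/13% of the remaining runs, against 7.9/18.5/25.0/39.2% printed.
- *Continue at 1.6 mg/kg.* 1.6 mg/kg is selected in about 7-8/16-19/23-27/34-39%, close to the printed row. But 5 mg/kg in Scenario 2 is about 0.19-0.21 with one-level escalation and up to 0.29 with a wider cap, against 0.34 printed. The Monte Carlo SE near 0.29 is √(0.29 × 0.71/1000) = 0.014, so even the nearest value is about 3.5 SE away. The setting that gives 0.29 (100% cap) also selects 2.4 mg/kg in about 6% of Scenario 2 runs, against 15.5% printed.

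No setting tried reproduces the table.

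**Step 5: internal checks of Table 3.** The true MTD in Scenario 3 is 4 mg/kg. Toxicity-band selections below it are 0.250 + 0.209 + 0.257 = 0.716, printed 0.611. For 3+3 they are 0.258 + 0.208 + 0.242 = 0.708, printed 0.671. The Scenario 4 3+3 column sums to 0.394 + 0.233 + 0.177 + 0.135 + 0.071 = 1.010, and its below-MTD entries to 0.804, printed 0.818.

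**Step 6: effect on the comparison with 3+3.** Printed true-MTD selection is 40.4/34.0/22.0/14.3% for toxicity-band and 33.3/21.8/20.9/13.5% for 3+3. With one-level escalation, stopping at an empty set gives about 31-33/17-18/20-21/13%, which is no advantage over 3+3. Continuing at 1.6 mg/kg gives about 19-21% in Scenario 2, again no higher than 21.8%. With a wider cap Scenario 2 rises to about 23-29%, above 3+3 but still short of 34.0%.

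**The case against.** Three arguments deserve weight.

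First, the two stopping rules may be meant as exhaustive. An empty set would then not end a run, and the lowest simulated dose is the natural place to continue. With one-level escalation this also gives a mean sample size of 17.3/15.5/14.6/13.3, near the printed 17.5/16.0/14.2/12.8. This is a fair reading and may well be part of what was coded. It still needs to be written down, and it does not recover the 5 mg/kg entry in Scenario 2.

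Second, DLT-free patients at 0.2, 0.4 and 0.8 mg/kg might enter the model. With one at each level, 1/3 at 1.6 mg/kg gives 0.21 there, under the limit. But 2/3 still gives 0.57, so the set can still be empty. Attachment 10 describes those cohorts as reflected in the assumed rates, not as data.

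Third, the trial is not bound by the model. The investigators and sponsor may depart from it, undescribed situations go to a documented decision, and Table JOBA.3 has lower doses (0.8 mg/kg has a posterior overdosing probability of 0.20 after 1/3 at 1.6 mg/kg). This stands. A reader might infer that a first-cohort DLT would leave the trial without a way forward; the documents do not support that.

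**Conclusion.** The point holds as one of reproducibility. The printed rule, prior, grid and stopping rules do not generate Table 3's toxicity-band results. The gap opens in 14.3-34.1% of simulated trials at the first cohort alone. The first-cohort figures need no assumption beyond Attachment 10's own inputs; the comparisons in steps 4 and 6 also depend on the assumed escalation cap.

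Two stronger readings are tempting. One is that an undocumented simulator setting was certainly used. The documents do not establish this: the sums in step 5 show that parts of the table disagree with each other, so tabulation error is an equally open explanation. Unprinted here also means only that the protocol does not give the setting. The other is that the overdose-control statement is false; no calculation here shows that. What is shown is that the claim of a higher MTD selection rate depends on settings the reader cannot see: with one-level escalation it fails in Scenario 2 whether runs stop or continue at 1.6 mg/kg. For the continuing rule the shortfall is small (about 0.19-0.21 against a simulated 0.218), so it is best read as no advantage.

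The sponsor should correct this, but the effect on patient management is small.

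**What to change.** In Attachment 10, state:
- the model output when no dose meets the limit;
- the escalation cap and the doses the model considers;
- whether outcomes at 0.2-0.8 mg/kg enter the likelihood.

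Reconcile these statements with Sections 6.2 and 7.2.2.3 and SAP Section 5.3. The choices remain with the sponsor and investigators.

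Then rerun Table 3 under exactly those settings, with a separate row for no admissible dose for both methods. Correct the Scenario 3 below-MTD row and check the Scenario 4 3+3 column. Limit the statements in Section 10.1 and the Attachment 10 Summary to what the rerun shows.

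The cost is a rerun of existing simulations and some wording; no change to trial conduct is asked for. The restated figures may be less favourable to the toxicity-band method.

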Attachment 11. Protocol JOBA Alterations for FGFR3

Such as the following FGFR3 alterations:

R248C

S249C

G372C

Y375C

K650E

K652E

FGFR3-TACC3 fusion

t(4;14)(p16.3;q32.3)

Attachment 12. Protocol Amendment I7O-MC-JOBA(a) Summary

A Phase 1 Study of LY3076226, a Fibroblast Growth Factor Receptor 3 (FGFR3) Antibody-Drug Conjugate, in Patients with Advanced or Metastatic Cancer

Overview

Protocol I7O-MC-JOBA, A Phase 1 Study of LY3076226, a Fibroblast Growth Factor Receptor 3 (FGFR3) Antibody-Drug Conjugate, in Patients with Advanced or Metastatic Cancer, has been amended. The new protocol is indicated by Amendment (a) and will be used to conduct the study in place of any preceding version of the protocol.

The overall changes and rationale for the changes made to this protocol are as follows:

- As requested by the Food and Drug Administration (FDA), patients with preexisting corneal diseases that may interfere with assessment of potential toxicity in the eyes during the study have been excluded in Section 6.1.2.
- As requested by the FDA, patients with skin disorders (for example, erythema, dermatitis) of \geq Grade 2 have been excluded in Section 6.1.2.
- As requested by the FDA, in reference to patients who may have refused standard therapy, wording has been added to Section 6.1.1 to state that these patients must be well informed about the benefit and risk of the standard therapy before signing the informed consent.
- As requested by the FDA, dose-limiting toxicity criteria (DLT) in Section 7.2.2.1 have been revised to indicate that the following events considered at least possibly related to LY3076226 will be DLTs: Grade 3 fatigue lasting >5 days, Grade 3 elevations in AST or ALT lasting >7 days, and concurrent elevation of ALT $>3 \times$ ULN and total bilirubin $>2 \times$ ULN in the absence of biliary obstruction or other causes that could reasonably explain the elevation. In addition, wording was added to Section 7.2.2.1 and Section 6.3.1 to indicate that significant related toxicity resulting in a >14 -day delay in starting Cycle 2 would be considered a DLT.
- As requested by the FDA, infusion duration information was added to Section 7.2.1.
- As requested by the FDA, clarification that premedication is not permitted for the initial dose of LY3076226 for each patient was added to Section 7.2.1.
- As requested by the FDA, clarification on expanding one-patient cohorts when Grade 2 or greater events considered at least possibly related to study drug are observed has been added to Section 7.2.2.3.

- As requested by the FDA, Section 8.1.4 has been modified to indicate that patients who have a concurrent elevation of ALT $>3 \times$ ULN and total bilirubin $>2 \times$ ULN and who, following assessment by the investigator, have no evidence of biliary obstruction or other causes that can reasonably explain the concurrent elevation, will be discontinued from the study. Additionally, Section 7.2.2.1 was revised as noted above for consistency with Section 8.1.4.
- As requested by the FDA, additional ophthalmic examinations as clinically indicated at the ophthalmologist's discretion were added to Section 8.1.4 and Attachment 1.
- As requested by the FDA, information about FGFR3 alteration types has been added in Attachment 11 and is referenced in Section 6.1.1 Inclusion Criteria.
- As requested by the FDA, a section has been added to specifically address the RP2D determination, Section 7.2.4.
- As requested by the FDA, wording regarding avoidance of strong inducers and inhibitors of CYP3A and strong inhibitors of CYP2D6A has been added to Section 7.5.
- Additional minor changes were made to increase the clarity and consistency of the document and to correct typographical errors.

Revised Protocol Sections

Note: All deletions have been identified by ~~strikethroughs~~.
All additions have been identified by the use of underline.

4. Abbreviations and Definitions

Term	Definition
C1D1	Cycle 1, Day 1
FDA	Food and Drug Administration
RP2D	recommended Phase 2 dose

